## 2.4 Adjustment for Multiple Centers

The study randomization is stratified by country of the investigative site, and only investigative centers from Japan and the United States are included in the study. The number of patients to be randomized in each country is not fixed, so there may be low enrollment in one of the countries. The stratification variable “country” will not be included in the statistical model by default. If there are at least 15 patients enrolled in each country, analyses that include a fixed effect for country may be performed as exploratory analyses.

## 2.5 Interim Analysis and Adjustment for Multiplicity

There were no planned formal interim analyses for this study. The interim review of the ongoing study data, that is described in [Section 2.1](#), does not include any alpha-spending nor will any modifications of the current study be contemplated.

The primary efficacy analyses include separate comparisons of each baricitinib arm to the placebo arm. To control the type 1 error rate for the primary efficacy analyses, these separate comparisons will be performed in a stepwise fashion. The 4-mg baricitinib arm will be compared with the placebo arm; if this test is statistically significant at level  $\alpha = 5\%$ , then the 2-mg baricitinib arm will be compared with the placebo arm; again using  $\alpha = 5\%$ .

Because this is a phase 2 study, no other adjustments for multiplicity will be made for statistical tests.

## 2.6 Coding of Concomitant Medications and Adverse Events

Adverse events (AEs) will be coded using the Medical Dictionary for Regulatory Activities (MedDRA™), and concomitant medications will be coded using the World Health Organization Drug Dictionary. The most recent version of these dictionaries at the time of database lock will be used for reporting. The version of the dictionary used for reporting will be provided in the CSR.

## 2.7 Definition of Study Time Points

Study baseline for a patient will extend from the date of informed consent until the date of first dose of randomly assigned study medication. For efficacy, safety and background characteristics, the baseline value of a parameter will be the last measurement of that parameter during the baseline period.

The post-baseline period will start on the date of first dose of randomly assigned study medication. Study day will be defined as

$$\text{Study Day} = \text{Date} - \text{Date of 1}^{\text{st}} \text{ dose} + 1 * \text{if} (\text{Date} \geq \text{Date of 1}^{\text{st}} \text{ dose}).$$

The last part of the equation indicates that 1 is added if the date of collection/observation is greater than or equal to the date of first dose of randomly assigned study medication. This forces all post-baseline events to have a positive value and all dates prior to first dose to have a value less than 0.

## 2.8 Reporting Conventions

This section details the general conventions to be used for the statistical analyses. Departures from these general conventions will be provided in the specific detailed sections of this analysis plan. The following conventions will be applied to all data presentations and analyses:

- Data will be summarized for the following groups:
  - Overall, Placebo, 2mg LY, 4mg LY will be used for patient accounting and disposition
  - Placebo, 2mg LY, and 4mg LY for all presentations except patient accounting and disposition
- Continuous variables will generally be summarized by the number of patients, mean, standard deviation, median, minimum, and maximum. Exceptions to these conventions will be specifically noted. Categorical variables will be summarized by the number and percentage of patients within each category.
- All mean and median values will be formatted to one more decimal place than the measured value.
- Standard deviation values will be formatted to two more decimal places than the measured value.
- Minimum and maximum values will be presented with the same number of decimal places as the measured value.
- The number and percent of responses will be presented in the form XX (XX %), where the percentage is in parentheses. Percentages will be rounded to the nearest percent. In the case of a frequency of zero, the frequency and percentage will be presented as 0 rather than 0 (0%).

- All summary tables will include the analysis population sample size (i.e., number of patients) in each treatment group.
- Date variables will be formatted as ddMMYY for presentation.

## **2.9 Changes to the Planned Analyses**

### ***2.9.1 Changes to the Planned Analyses in the Protocol***

- There was a typo for the analyses of continuous secondary efficacy endpoints. The level for the confidence intervals should have been 95%, rather than 90%. The correction has been implemented in this SAP.

## **3 Patient Accounting and Disposition**

### **3.1 Patient Accounting**

For each study center the number of patients in the ITT, Safety and PK populations will be provided overall and by randomized assignment. The date of the first patient visit and the last patient visit for each study center will also be provided. These dates and patient totals will also be summarized for the whole study and by country.

A list of protocol violations that could potentially impact the analysis of the study will be determined during the conduct of the study by study team members who are blinded to assigned study treatment. The number and percentage of patients with each violation will be tabulated overall and by randomized treatment assignment.

### **3.2 Study Disposition**

The disposition of all randomized patients will be presented. The number of patients randomized and the number of patients in the Safety Population will be presented overall and by treatment group. In addition, the reason for study discontinuation will be tabulated by treatment group using the list of reasons provided in the eCRF. This report will be generated for both the overall population and for patients enrolled in Japan.

## **4 Baseline Characteristics**

Demographic data, baseline characteristics, and atopic dermatitis history will be summarized using descriptive statistics by randomized treatment assignment. These summaries will be based on the ITT population and will be generated using both the overall population and for patients enrolled in Japan. Randomized patients who are missing measurements of the baseline variable being analyzed will not be included in the summary for that variable.

Unless otherwise specified, F-tests from the analysis of variance (ANOVA) model with a fixed effect for randomized treatment group will be conducted for continuous variables. These tests will be based on the Type 3 sum of squares. Categorical variables will be analyzed using the general association chi-square tests. If the number of patients in a category is less than 5 for either randomized group, Freeman-Halton exact tests will be used instead of the chi-square test.

## 4.1 Demographics

Demographic variables collected prior to randomization include date of birth, sex, race, and ethnicity. Age at study entry, age group (Age < 65 years, Age ≥ 65 years), sex, and race will be summarized and reported. Age at study entry will be based on the age of the patient on the date the informed consent is signed. Age at study entry will be analyzed as a continuous variable while age group is analyzed as a categorical variable. Sex will also be analyzed as a categorical variable. Patient race will be captured using multiple racial categories (i.e., American Indian or Alaskan Native, Asian, Black or African American, Native Hawaiian or other Pacific Islander, and White), and Race will be reported using a chi-square test and these categories along with a 'Multiple' category for those patients who identify more than one race category. The response for ethnicity could be Hispanic or Latino, or Non-Hispanic or Latino. Ethnicity will be analyzed as a categorical variable.

## 4.2 Baseline Anthropometrics

Patient height and weight will also be collected prior to randomization. Both variables will be reported in metric units (height in cm and weight in kg) and will be analyzed as continuous variables along with Body Mass Index (BMI; in kg/m^2). Body mass index will also be analyzed categorically using the categories obese (BMI ≥ 30 kg/m^2) and non-obese (BMI < 30 kg/m^2).

## 4.3 Baseline Habits

The alcohol, tobacco, and caffeine habits for each patient will be collected during the baseline period. The number and percentage of patients who consume alcohol, tobacco and caffeine will be tabulated for each treatment group using the ITT population. In addition, among those patients who currently smoke descriptive statistics of the number of cigarettes per day will be provided by treatment group. No statistical inference will be performed for the habits variables, and this report will only be produced for the overall population.

## 4.4 Atopic Dermatitis History

The date of atopic dermatitis diagnosis along with the types of prior therapies received will be collected during the screening period. The types of prior therapy will be collected using the following categories: hydration plus topical steroids and/or antibiotics (Category 1), systemic steroids and/or phototherapy (Category 2), cyclosporine and/or other immunomodulators (Category 3). Patients could have received treatments from more than one category.

Time since diagnosis of atopic dermatitis, in months, will be descriptively summarized and analyzed as a continuous variable. Since patients could have received treatments from multiple categories, each category will be analyzed separately as a categorical variable. In addition, the number and percent of patients who reported alopecia areata in their medical history will be compared between treatments using the general association Mantel-Haenszel or Freeman-Halton statistic.

## 5 Concomitant Medications

Concomitant medications will be defined as medications, other than triamcinolone 0.1% cream, taken on or after the date of first dose of randomly assigned study treatment. This includes all medications initially taken prior to the date of first dose of randomly assigned study medication but with a stop date that is either missing or after the date of first dose of randomly assigned study medication. Those medications where the stop date is documented as prior to the date of first dose of randomly assigned study medication will be classified as prior medications. The prior medications will not be included in any summary reports.

The reporting of concomitant medications will be by WHODD preferred drug name (often the generic drug name). The report of all concomitant medications taken during the study will be prepared by treatment using the safety population, and the number and percentage of patients who received each concomitant medication will be presented.

## 6 Efficacy Analyses

Efficacy analyses for this study will be based on the findings from clinical tools (EASI, SCORAD, and IGA) and patient reported outcomes (DLQI, Itch NRS, and POEM) that assess the extent and severity of atopic dermatitis, the symptoms related to atopic dermatitis, or the impact on the patient's quality of life (QOL). In addition, data from wearable actigraphy devices will be analyzed to assess sleep/wake patterns and changes in nocturnal itch patterns. All of these assessments will be collected longitudinally during the study.

All efficacy analyses will be performed using the ITT population. Reports will be generated for the overall population, and many of the reports will also be produced using only patients enrolled in Japan. The method of analysis or statistical technique employed to address missing data will be described separately for each variable. Presentations of efficacy will include the number of patients with data at each time point plus related statistics derived from the analysis.

Assessments performed at Visit 2 will be considered the baseline measurements. If the Visit 2 assessment for a clinical tool or patient reported outcome is missing, then the Visit 1 assessment, if it exists, will be considered the baseline measurement. If a patient has no assessment of a clinical tool or patient reported outcome prior to the initiation of study treatment, then the patient will be excluded from the efficacy analysis of that variable at the given time point.

### 6.1 Primary Efficacy Analysis

The primary efficacy analysis will be based on the Eczema Area and Severity Index (EASI), which is a valid and internally consistent clinical observation tool that has adequate intra-observer reliability, intermediate inter-observer reliability, and adequate responsiveness.

The EASI assesses objective physician estimates of two dimensions of atopic dermatitis – disease extent and clinical signs – by scoring the extent of disease (percentage of skin affected: 0 = 0%; 1 = 1-9%; 2 = 10-29%; 3 = 30-49%; 4 = 50-69%; 5 = 70-89%; 6 = 90-100%) and the severity of four clinical signs (erythema, induration/papulation, excoriation, and lichenification) each on a scale of 0 to 3 (0 = none, absent; 1 = mild; 2 = moderate; 3 = severe) at four body sites (head and neck, trunk, upper limbs, and lower limbs). Half scores are allowed. Each body site will have a score that ranges from 0 to 72, and the final EASI score will be obtained by weight-

averaging these four scores (using multipliers 0.2 for head and neck and upper limbs and 0.3 for trunk and lower limbs). Hence, the final EASI score will range from 0 to 72 for each time point.

The EASI will be assessed at baseline and at Weeks 1, 4, 8, 12, and 16 post-randomization, plus at the early termination visit, if applicable. At each of the post-baseline visits the EASI will be computed, and the EASI score will be compared with the EASI score obtained at baseline to obtain the proportion of reduction.

The primary efficacy measure will be the proportion of moderate-to-severe atopic dermatitis patients achieving a 50% reduction in the Eczema Area and Severity Index, or EASI-50, after 16 weeks of treatment. The primary analysis will be performed using a Non-Responder Imputation (NRI) analysis. All patients with a less than 50% reduction in the EASI at Week 16, plus all patients who either discontinue study treatment or discontinue from the study for any reason at any time prior to Week 16 will be defined as non-responders for the NRI analysis. Randomized patients without at least 1 post-baseline observation of EASI will also be defined as non-responders for the NRI analysis.

The proportion of patients achieving EASI-50 in the placebo arm will be compared to the proportion of patients in each of the baricitinib arms (2 mg and 4 mg) using a two-sided chi-square test with  $\alpha=0.05$ . To control for multiplicity testing will be performed in a stepwise fashion. First, the 4-mg baricitinib arm will be compared with the placebo arm; if this test is statistically significant, then the 2-mg baricitinib arm will be compared with the placebo arm.

The number and percent of patients, based on an NRI analysis, with a 50% reduction in EASI will be presented for each treatment arm at each time point including the patient's last assessment, which should be either Week 16 or the early termination visit. The p-values for the pairwise chi-square tests from the NRI analyses will also be tabulated. In addition, a bar chart that shows the percentage of patients with a 50% reduction in EASI for each treatment arm at each time point including the patient's last assessment will be presented. The figure displays will be generated for the overall population and by country – United States and Japan.

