### 1.3 Determination of Sample Size

Approximately 120 patients will be enrolled using a 4:3:3 randomization scheme for placebo, 2 mg baricitinib, or 4 mg baricitinib, respectively. Assuming a drop-out rate no greater than 20%, approximately 96 patients will complete the study.

This sample size provides 90% power to detect a 35% difference in EASI-50 between placebo and either the 4-mg baricitinib using a 2-sided chi-square test with  $\alpha = 0.05$ .

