## 2 General Statistical Methodology and Conventions

CHORUS will designate a provider to generate the statistical analyses detailed in this SAP. All computations for statistical analyses will be performed using SAS® software, Version 9.3 or later. All SAS programs used in the production of statistical summary outputs will be validated with independent programming prior to finalization. In addition, all program outputs will be independently reviewed. The validation process will be used to confirm that all data manipulations and calculations were accurately done. Once validation is complete, a senior statistical reviewer should perform a final review of the documents to ensure the accuracy and consistency with this plan and consistency within tables. Upon completion of validation and quality review procedures, all documentation will be collected and filed by the project statistician or designee.

Before implementation of parametric methods of analysis, the distribution of analysis variables will be examined to determine if model assumptions are satisfied. Transformations or nonparametric methods of analysis may be used if warranted. However, in some cases, nonparametric analysis may be the initially proposed method due to the expected distribution of response. Whenever alternative methods of analysis are required, the description of the new method along with the rationale for its use will be documented in the CSR.

The eCRF data for all patients will be provided in Standard Data Tabulation Model (SDTM) datasets. Any additional data listing supplied as part of the CSR will be sorted by investigative site and patient identification number, and patients will be identified in the listings by the investigator number concatenated with the patient number.

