### 2.1 Randomization Schedule and Unblinding Plan

This is a double-blind study in which the patients, investigator, and study site personnel will be blinded to treatment allocation. PAREXEL International will be responsible for building the interactive response technology (IRT) system that randomly assigns study treatments to patients.

To preserve the blinding of the study, only a minimum number of Lilly personnel will see the randomization table and treatment assignments before the study is complete. A limited group may have access to unblinded treatment information to ensure the safety of patients in the study. Another small team of Lilly scientists (project statistician, statistical analyst, pharmacokineticist,

research physician, medical director, and global patient outcome scientist) will have access to the unblinded treatment information just before the last patient has completed their Week 12 visit. Their review of the unblinded data will facilitate planning of future studies. They may communicate unblinded findings to a small number of other Lilly personnel to facilitate business decisions, but not to those who are involved in the conduct of the study who would be involved in direct site contact and assessment of blinded clinical outcomes. A list of all those individuals who become unblinded prior to study completion will be maintained by the unblinded statistician. This process will ensure that data integrity is maintained while patients are still receiving blinded therapy.

Once the last patient completes Week 16, thus blinded study treatment, and all data management data activities have been completed – data entered, coding completed, and all queries resolved – the Chorus Asset Manager and Statistician will approve PAREXEL to release the randomization schedule to the reporting team. Additional Lilly personnel as well as steering committee members may also be unblinded to commence reporting of results from the treatment period. Site personnel and those Lilly personnel who are involved in the conduct of the study who would be involved in direct site contact and assessment of blinded clinical outcomes and patients will remain blinded until the study completes.

Emergency unblinding of site personnel may be performed through the IRT system. This option may be used ONLY if the patient's well-being requires knowledge of the patient's treatment assignment. All calls resulting in an unblinding event are recorded and reported by the IRT system.

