### 6.2.2 *SCORing Atopic Dermatitis (SCORAD)*

To determine disease severity the SCORing Atopic Dermatitis (SCORAD) index uses the rule of nines to assess disease extent (head and neck 9%; upper limbs 9% each; lower limbs 18% each; anterior trunk 18%; back 18%; genitals 1%; and hands 2%) and evaluates six clinical characteristics – erythema, edema/papulation, oozing/crusts, excoriation, lichenification and dryness – each on a scale of 0 to 3 (0 = none, absent; 1 = mild; 2 = moderate; 3 = severe). SCORAD also assesses subjective symptoms of pruritus and sleep loss with visual analogue scales (VAS) where 0 is no itch (or no sleeplessness) and 10 is the worst imaginable itch (or sleeplessness). These three aspects: extent of disease (A: range 0-102), disease severity (B; range 0-18) and subjective symptoms (C: range 0-20) will be combined using,  $A/5 + 7*B/2 + C$ , to give a maximum possible score of 103.4.

The SCORAD will be assessed at baseline and at Weeks 1, 4, 8, 12, and 16 post-randomization, plus at the early termination visit, if applicable. At each of the post-baseline visits the SCORAD will be computed, and the SCORAD score will be compared with the SCORAD score obtained at baseline to obtain change and percent change from baseline. Descriptive statistics for the SCORAD value and the subjective assessments of pruritus and sleep loss and the respective changes from baseline will be tabulated for each time point using the overall and by-country populations.

The MMRM and ANCOVA analyses described in [Section 6.2.1](#) will be performed to compare the baricitinib treatment arms and placebo for change and percent change from baseline in the SCORAD score, and change from baseline in the pruritus and insomnia assessments. The tabular outputs for the MMRM and ANCOVA analyses described will be provided.

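### Are the EASI multipliers in SAP section 6.1 wrong because head and neck counts as much as both upper limbs?

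*SAP*

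**What the plan says.** Section 6.1 of the SAP scores four body sites for extent (0 to 6) and for four signs (0 to 3 each): "Each body site will have a score that ranges from 0 to 72". The total is a weighted average of the four site scores, "using multipliers 0.2 for head and neck and upper limbs and 0.3 for trunk and lower limbs", and the section closes the derivation with "Hence, the final EASI score will range from 0 to 72 for each time point". No source is cited for the multipliers. The only entry in the reference list concerns intention to treat.

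The only regional body-area figures in the SAP are in section 6.2.2, where they define the extent component of SCORAD: "head and neck 9%; upper limbs 9% each; lower limbs 18% each; anterior trunk 18%; back 18%; genitals 1%; and hands 2" percent, with "extent of disease (A: range 0-102") as the resulting range.

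Section 2 provides for independent programming, after which "a senior statistical reviewer should perform a final review of the documents to ensure the accuracy and consistency with this plan".

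**The concern.** Every site is scored on the same 0 to 72 scale whatever its size, so if region size is to enter the EASI total at all, it must do so through the multipliers. On the section 6.2.2 figures head and neck is half the size of the upper limbs taken together, yet section 6.1 weights the two equally. Head and neck is the one site that stands far from its body-area share.

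The SAP's own range statement gives no protection, because any four weights that sum to 1 yield 0 to 72. Double programming against the text of section 6.1 would carry a wrong set through unchanged.

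The multipliers feed EASI-50, EASI-75, EASI-90 and the change and percent change in EASI. If they were not those of the instrument, the reported response rates would not be EASI response rates. The unblinded team described in section 2.1 would also take them into later work: "Their review of the unblinded data will facilitate planning of future studies".

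**Working it through.** **1. The plan's own figures.** Site maximum = 6 × (4 × 3) = 72. Sum of multipliers = 0.2 + 0.2 + 0.3 + 0.3 = 1.0. EASI maximum = 1.0 × 72 = 72, as section 6.1 states. For SCORAD, 9 + 18 + 36 + 18 + 18 + 1 + 2 = 102, and 102/5 + 7 × 18/2 + 20 = 103.4, both as section 6.2.2 states. Each section agrees with itself.

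**2. The comparison that raises the doubt.** Take the section 6.2.2 figures for the four EASI sites (9, 18, 36, 36; sum 99) and divide each multiplier by the share.

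| Site | 6.1 multiplier | 6.2.2 share | Ratio |
|---|---|---|---|
| Head and neck | 0.2 | 9/99 = 0.091 | 2.20 |
| Upper limbs | 0.2 | 18/99 = 0.182 | 1.10 |
| Trunk | 0.3 | 36/99 = 0.364 | 0.825 |
| Lower limbs | 0.3 | 36/99 = 0.364 | 0.825 |

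None of the four ratios is 1. The multipliers are therefore not a rule-of-nines set with one misprinted entry, and the rule of nines cannot tell us what the EASI set should be.

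**3. What a different set could do to one patient.** The site scores below are constructed. Order: head and neck, upper limbs, trunk, lower limbs. Reduction = 1 − (weighted Week 16 score)/(weighted baseline score).

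- Baseline 20 in every site, Week 16 at 20/8/8/8. Section 6.1: (4 + 1.6 + 2.4 + 2.4)/20 = 10.4/20, reduction 48.0%. Area shares: (180 + 144 + 288 + 288)/99 = 9.09, reduction 54.5%.
- Same baseline, Week 16 at 0/10/11/12. Section 6.1: 8.9/20, reduction 55.5%. Area shares: 10.18/20, reduction 49.1%.
- Same baseline, Week 16 at 10/10/10/10: 50% under both.

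Status can flip in either direction, but only when sites respond unevenly. If every site falls by the same proportion, any weights give the same reduction.

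**4. What it could do to the trial.** The derivation is the same in every arm. With no treatment effect the site scores have the same distribution in each arm, so response rates are equal under any fixed weights and type I error does not depend on the choice.

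For the size of the effect, an illustrative simulation used the 35-point difference and 20% drop-out of section 1.3 ("Assuming a drop-out rate no greater than 20%, approximately 96 patients will complete the study"), with drop-outs as non-responders. All else is assumed:

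- log-normal baseline site scores with median 20 and log-SD 0.5;
- log-ratio SD 0.8;
- between-site correlations of 0.3 or 0.6 at baseline and 0.3 to 0.9 for response;
- placebo response 10, 25 or 40%.

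With sites responding alike on average, 0.5 to 5.0% of completers change status and a 35.0-point difference becomes 35.0 to 35.9. With head and neck assumed to respond less (log ratio +0.3), the figures are 0.7 to 6.1% and 34.1 to 37.2 points.

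**5. What steps 3 and 4 do not measure.** Both treat the SCORAD shares as if they were the true EASI weights. The SAP gives no ground for that, so these figures describe the gap between two weightings and not a bias.

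**The case for a change.** The strongest case for acting is that the check is cheap, the endpoint is primary, and this SAP is not free of slips:

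- section 7.1.1 subtracts the last-dose date from the first-dose date;
- section 7.2.7 glosses thrombocytopenia as a fall in red cells;
- the abbreviation list expands AST as alanine aminotransferase;
- section 6.2.1 keeps a 90% interval for the ANCOVA although section 2.9.1 says the level was corrected to 95%.

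An unsourced set of multipliers in such a document, with one entry out of line, deserves a second look. The usual programming checks would probably not supply it.

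Much of this stands. The arithmetic is right, there is no citation, and neither the range statement nor double programming to the text would reveal a wrong split. But each of those other slips can be seen from the SAP itself, by its own logic or by a conflicting sentence. The multipliers cannot: no sentence conflicts with them and their arithmetic closes. Whether they are right depends wholly on the EASI scoring instructions, which the SAP does not reproduce.

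The missing citation carries little weight by itself. SCORAD, DLQI, POEM and QIDS-SR16 scoring are also given without a reference, and section 1.1 sends the reader to the protocol for procedures and assessments.

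**Conclusion.** No change to the plan follows. Section 6.1 states a complete and arithmetically consistent rule, and the only thing set against it is the extent measure of a different index. The SAP nowhere says that EASI multipliers should equal body-area shares. What remains is a missing reference: a detail that the statistician deriving EASI would settle by looking at the scoring instructions in use, without altering any analysis.

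This does not certify the multipliers as correct. The conclusion is that the document does not show them to be wrong. It rests on reading the SAP alone and would have to be revisited if the trial's scoring instructions gave another set.

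On size: individual patients with uneven regional response could be classified differently under another weighting, type I error is unaffected, and on the assumed inputs above the between-arm difference moves by about 2 points at most (37.2 − 35.0 = 2.2).
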